7.2.1 Adverse Event Severity

The intensity or severity of each Adverse event must be assessed according to the following classifications:

Mild	Awareness of signs, symptoms, or events that are otherwise easily tolerated that may result in minimal transient impairment of body function or damage to a body structure, but do not require intervention other than monitoring.
Moderate	Any event that results in moderate transient impairment of body function or damage to a body structure that causes interference with usual activities, or that warrants possible intervention, such as the administration of medication, to prevent permanent impairment of body function or damage to body structure.
Severe	Any event that is incapacitating (an inability to do usual activities) or is life-threatening and results in permanent impairment of body function or damage to a body structure, or requires intervention, such as major surgery, to prevent permanent impairment of body function or damage to a body structure.

7.2.2 Adverse Event Causality Assessment

The clinician who examines and evaluates the enrolled subject will determine the AE's causality based on temporal relationship and his/her clinical judgment. The degree of certainty about causality will be graded using the categories below.

Causality	Definition of causality
Causal relationship	The event is associated with the investigational device beyond reasonable doubt.
Probable	The relationship with the use of the investigational device seems relevant and/or the event cannot reasonably be explained by another cause, but additional information may be obtained.
Possible	The relationship with the use of the investigational device is weak but cannot be ruled out completely.
Unlikely	The relationship with the use of the investigational device seems not relevant and/or the event can be reasonably explained by another cause, but additional information may be obtained.
Not related	Relationship to the investigational device can be excluded.

IGT Systems	Clinical Research Protocol Next Generation X-ray Imaging System (NEXIS)	Doc ID: XCY612-130814 Rev: 01 Page 32 of 57
-------------	----------------------------------------------------------------------------	---------------------------------------------------

7.2.3 Adverse Event Outcome

The outcome of each Adverse Event must be assessed according to the following classification.

Outcome classification	Definition
Recovered/Resolved	Subject fully recovered with no observable residual effects
Recovered/Resolved with sequelae	Subject recovered with observable residual effect
Recovering/Resolving	Subject's condition improving, but residual effects remain
Not Recovering/Not Resolved	AE is ongoing without improvement in the overall condition
Fatal	Subject died as a result of the AE (whether or not the AE is related to the investigational device)
Unknown	AE outcome is unknown (e.g., subject is lost to follow-up)

7.3. Anticipated adverse device effects

Anticipated adverse device effects are described below in Table 4

Anticipated adverse device effects	Likely incidence	Mitigation or treatment
Side effects of additional X-ray dose	PoH 1	
The brain is quite insensitive to radiation exposure: weighting factor of 0.01 when calculating effective organ doses (29), and sensitivity to stochastic radiation effects decreases with age (30).
 
To ensure that the risks of additional radiation is minimized, no subject under the age of 50 will be included in the study.

Side effects of additional Iodine contrast	PoH 1	
An absolute GFR (aGFR) and non-renal risk factors for CI-AKI will be assessed before administering iodine contrast agent. These measures will ensure that the risks associated with iodine contrast agents will be minimized.

Dose control functionality fails, causing more radiation than expected	PoH 2	Tests are implemented
Poor scan quality if slower XperCT scan results in motion artifacts	PoH 2	
Add guidance in the IFU to guide scan selection in case a fast scan is required. The Allura product also has a 20s neuro scan and the user can use a faster non-spectral scan when needed.

Table 4 Anticipated adverse device effects.

7.3 Clinical Event Committee (CEC)

Clinical Events Committee (CEC) & Event notification

An independent board consisting of radiologists, hospital physicists and stroke physicians who are not participating in the study will adjudicate serious adverse events in the trial.

The role of the CEC will be to:

- Adjudicate any SAE that could be attributable to ionizing radiation.

IGT Systems	Clinical Research Protocol Next Generation X-ray Imaging System (NEXIS)	Doc ID: XCY612-130814 Rev: 01 Page 33 of 57
-------------	----------------------------------------------------------------------------	---------------------------------------------------

- Adjudicate whether an SAE is deemed attributable to the procedure or is from the natural course of the standard research protocol or stroke illness.
- Continuous evaluation of available external data and/or knowledge, as presented at major congresses and /or published in peer-reviewed journals, which may have an impact on the study or be considered a protocol violation.
- The CEC role does not interfere with the sponsor's responsibility to classify and report adverse events to competent authorities.

7.4. Unavoidable adverse events

Not applicable since only a scan will be acquired.

8. Statistical considerations

Any departure or deviation from these planned statistical methodologies will be documented and discussed in the Statistical Analysis Plan that will include the statistical rationale for change.

8.1. Image data management

The raw image data with added dual energy properties (DE-CBCT) will be processed using novel reconstruction and segmentation techniques. During the intervention only the product reconstruction algorithm is available for raw image data acquired by the first layer of the detector and images reconstructed in this fashion will be identical to current CBCT.

After the intervention the DE-CBCT raw image data will be reconstructed with the novel spectral reconstruction software and then evaluated by three independent neuroradiologists (not involved in the clinical investigation) for subjective outcome variables. The first cases will also be used to iterate and optimize reconstruction algorithms. Images will be processed on-site and off-site. For ordinal outcome variables comparing the subjective performance of DE-CBCT and CBCT to CT, CTA and CTP (such as the first secondary objective), neuroradiologists will have access to both DE-CBCT and reference image data concurrently. For the primary and second secondary objective DE-CBCT and reference image, data will be cleaned from any information regarding acquisition technique and evaluated randomly and separated in time, in order to limit the possibility of bias.

A secure image data repository will be set up at Karolinska University Hospital, the access to which will be provided through IntelliSpace Discovery (ISD) that will serve as the interfacing client for managing and logging the access of data by authorized personnel involved in this study. No additional software will be required by the user to access the data as the ISD client runs in chrome web browser with a zero footprint i.e., no data will be stored on user's computer while using the ISD interface.

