8.7. Secondary objectives

8.7.1. Vessel tree visibility

Endpoint (1st Secondary endpoint)

Proportion of contrast-enhanced DE-CBCT rated non-inferior (i.e. equal or superior) vessel visibility compared to CTA (reference standard).

Applicable subjects

All subjects with a contrast enhanced DE-CBCT scan and diagnostic CT angiography.

Data

- Radiologist rating
 - Inferior/Equal/Superior
 - Distal ICA (dICA)
 - A1-A2
 - Lenticulostriate arteries

IGT Systems	Clinical Research Protocol Next Generation X-ray Imaging System (NEXIS)	Doc ID: XCY612-130814 Rev: 01 Page 36 of 57
-------------	----------------------------------------------------------------------------	---------------------------------------------------

- M1
- M2
- M3-M4
- Distal Vertebrales
- Basilar
- Basilar perforating branches
- AICA-PICA-SCA
- P1-P2

Analysis

Images are evaluated by radiologists using CT angiography as reference standard and the proportion of equal or superior vessel visibility rating in abovementioned vessel territories is defined.

Hypothesis:

$$\begin{aligned} H_0: \pi_2 &\leq 0.80 \\ H_1: \pi_2 &> 0.80 \end{aligned}$$

Where π_2 is the observed proportion of equal or superior vessel visibility and 0.80 is the performance goal.

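### No masking is stated for the vessel-visibility reading (first secondary endpoint), although section 8.1 masks the readings for the other two formally tested endpoints

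*Combined protocol and SAP*

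**What the plan says.** Section 8.1 (Image data management) describes two ways of reading the images.

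- **Ordinal comparative ratings.** The section gives an example of this class, "such as the first secondary objective", which is vessel tree visibility. Here "neuroradiologists will have access to both DE-CBCT and reference image data concurrently". Label removal, coding and randomised position are not mentioned.
- **Primary (ASPECTS) and second secondary (hemorrhage) objectives.** "For the primary and second secondary objective DE-CBCT and reference image, data will be cleaned from any information regarding acquisition technique", and the images are "evaluated randomly and separated in time, in order to limit the possibility of bias".

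In both cases the images are "evaluated by three independent neuroradiologists (not involved in the clinical investigation) for subjective outcome variables".

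Section 8.7.1 sets the vessel rating for each of 11 arterial territories on the scale "Inferior/Equal/Superior". On the analysis it says: "Images are evaluated by radiologists using CT angiography as reference standard and the proportion of equal or superior vessel visibility rating" is determined. The null hypothesis is that this proportion is at most 0.80. Section 8.2 gives the test a one-sided alpha of 0.0125, so this is a formally tested endpoint and not a descriptive one.

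**The concern.** The plan recognises reader bias and guards against it for two of its three formally tested endpoints. As written, the third has no such guard, yet it is a direct relative judgement of the new device against the established one. Section 8.1 itself describes ratings of this class as subjective.

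The scoring makes the endpoint sensitive. Equal and superior both count as success, so one step on the scale, from inferior to equal, turns a failure into a success. The reverse step turns a success into a failure. If readers know which image is DE-CBCT, their expectations can act at exactly that boundary. A larger sample would not remove such a bias. At stake is whether a pass or a fail on this endpoint can be credited to the images alone.

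**Working it through.** **Inputs**

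- Target proportion 0.90, performance goal 0.80, one-sided alpha 0.0125, power 80%, 126 regions, 11 regions per subject, 12 subjects (section 8.2).
- Success for a region means a rating of equal or superior (section 8.7.1).
- Size and direction of any rating shift: not in the documents, so assumed below and shown as a range.
- Independence of regions: assumed, as the plan's region-based sample size does.

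**Step 1. Reproduce the plan's figure.** With n regions and success at r or more, use the exact binomial tail P(X ≥ r | n, p). At n = 126 and p = 0.80:

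- P(X ≥ 110) = 2.2%, above 1.25%.
- P(X ≥ 111) = 1.18%, below 1.25%.

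The smallest valid pass mark is therefore 111 (111/126 = 88.1%). Power at 0.90 is P(X ≥ 111) = 80.9%. By this method 126 is the smallest n that reaches 80%, and 126/11 = 11.45 rounds up to 12 subjects. Both stated figures reproduce. The plan prints no pass mark; 111 is derived from its inputs.

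**Step 2. Favourable shift, true proportion 0.80.** If unmasked reading raises the proportion rated equal or superior by b, the pass probability is P(X ≥ 111 | 126, 0.80 + b). At 0.80, 20% of regions are truly inferior, so a shift b means that a fraction b/0.20 of them is rated equal.

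| Assumed shift b | Inferior regions re-rated (b/0.20) | Regions moved (126 × b) | False-success chance |
|---|---|---|---|
| 0 | 0% | 0 | 1.2% |
| 0.02 | 10% | 2.5 | 4.3% |
| 0.03 | 15% | 3.8 | 7.6% |
| 0.05 | 25% | 6.3 | 20.0% |

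A shift of about two to three regions in 126 more than triples the planned 1.25% error (4.3/1.25 = 3.4).

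**Step 3. Unfavourable shift, true proportion 0.90.** Readers used to CT angiography could instead be stricter with the new images. The pass probability is then P(X ≥ 111 | 126, 0.90 − b):

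- b = 0: 80.9%
- b = 0.02: 55.5%
- b = 0.05: 20.0%

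**Step 4. Full 12 subjects.** With 12 × 11 = 132 regions the pass mark is 116. The pass probability is 1.2% at 0.80, 21% at 0.85 and 83% at 0.90, so the picture is the same.

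**Step 5. Dependence between regions.** A beta-binomial model with 12 subjects of 11 regions, pass mark 116 and an assumed within-subject correlation of 0.2 gives 10% at 0.80 and 34% at 0.85. The starting level is higher, but a 0.05 shift still raises the chance of a pass markedly. Clustering is a separate matter and is not needed for this point.

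**The case against.** **Section 8.1 never says that labels are shown.** A reader might infer that the plan deliberately reveals the device to the readers. The text does not support that: it neither states that labels are kept nor excludes coded side-by-side reading. The revision history even describes the rewrite of 8.1 in terms that suggest a general intention to mask. The log does not govern the current text, and its difference from 8.1 is not an error. What stands is that masking is not specified here, while it is limited by name to the other two objectives. Since readers also grade against CT angiography as reference, they can be expected to know which image is which.

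**Size and direction of bias are unknown.** A reader might also infer that the result will be inflated, for instance by five points. Nothing in the documents gives that figure or says that readers would favour the device, and the shift could go the other way. This objection stands in full, which is why the figures above are a range under assumption.

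**The readers are independent.** This is a real partial safeguard, because it limits their interest in the outcome. It does not mask the device.

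**A comparative rating needs both images together.** Agreed. Viewing two images together does not require knowing their source.

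**Masking may fail.** Cone-beam images may be recognisable, and section 8.9.3 plans to rate artefacts near the skull base and in the posterior fossa, close to several of the rated vessels. This limits the gain. The same limit applies to the ASPECTS and hemorrhage readings, where the plan removes acquisition information all the same.

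**Proportion.** This is a secondary endpoint in an open-label, first-in-man proof-of-concept study, so the point is an inexpensive improvement and not a flaw that undermines the study.

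**Conclusion.** The point holds as a gap in specification. For a formally tested, subjective rating in which equal counts as success, section 8.1 states no masking, whereas it does so for the other two tested endpoints. This leaves a risk of reader bias; it does not show that bias will occur or which way it would run.

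The size is conditional on independent regions, 126 regions with success at 111 or more, and an assumed shift. At a true proportion of 0.80, favourable shifts of 0.02 to 0.05 raise the false-success chance from 1.2% to between 4.3% and 20%. At a true proportion of 0.90, equal shifts against the device cut power from 80.9% to between 55.5% and 20%. The sample size itself reproduces and needs no change.

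**What to change.** Keep concurrent viewing and add to section 8.1, for vessel visibility:

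- Each pair is shown as image A and image B, with acquisition labels and overlays removed.
- Position is randomised per case.
- Readers rate A against B for each territory, and the key is applied at analysis to convert the ratings to inferior, equal or superior for DE-CBCT.

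Section 8.7.1 should then say that CT angiography acts as the reference when the key is applied, not during the reading. Where feasible, use the same procedure for the other inferior/equal/superior ratings (sections 8.8.4, 8.8.5 and 8.9.2). If coded reading was already intended, a sentence saying so settles the matter.

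Do not require the same slice thickness or display preset for both images. That is a separate choice and could alter the spectral reconstruction being assessed.

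Cost: some set-up work for the reading. The documents do not say whether the image client can show coded, randomised pairs, so this needs checking. Images are processed and read after acquisition, so no patient procedure and no sample size changes. Masking will be imperfect where texture or artefacts give the modality away.

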8.2. Sample size justification

Statistical analyses will be performed by Karolinska University Hospital. This is a prospective, open label single centre study. A diagnostic study using DE-CBCT on confirmed acute ischemic or hemorrhagic stroke has not been done before. The sample size estimations aims to prove diagnostic quality non-inferiority compared to CT according to performance goals below.

The sample size for the primary endpoint is trait-based, using ten [10] ASPECTS regions for each subject. To evaluate the diagnostic accuracy of DE-CBCT compared to CT, it is estimated that a sample size of 137 is required to render a power of 90% (target accuracy of 0.90, performance goal lower boundary of 0.80, one-sided alpha of 0.025). For this endpoint, a minimum sample size of 14 subjects is required.

The first secondary endpoint (vessel tree visibility) is also trait-based, using eleven [11] arterial regions for each subject. To evaluate the proportion of regions rated equal or superior to CT, it is estimated that a sample size of 126 is required to render a power of 80% (target proportion of 0.90, performance goal lower boundary of 0.80, one-sided alpha of 0.0125, adjusted for multiple secondary endpoints). For this endpoint, a minimum sample size of 12 subjects is required.

IGT Systems	Clinical Research Protocol Next Generation X-ray Imaging System (NEXIS)	Doc ID: XCY612-130814 Rev: 01 Page 34 of 57
-------------	----------------------------------------------------------------------------	---------------------------------------------------

The second secondary endpoint is defined as diagnostic accuracy to determine the presence of intracranial hemorrhage, comparing DE-CBCT to CT (reference). The endpoint is subject-based and it is estimated that a sample size of 20 is required to render a power greater than 95% (target accuracy of 0.9999, performance goal lower boundary of 0.80, one-sided alpha of 0.0125, adjusted for multiple secondary endpoints). The sample size includes both subjects with hemorrhage and negative controls, preferably with 0.5 hemorrhage prevalence, with a threshold of at least a third of our subjects to have an intracranial hemorrhage. For this endpoint, a minimum sample size of 20 is required.

In total, the minimum sample size required is 20 subjects, of which two-thirds have ischemia, one-third have intracranial hemorrhage, and at least half must have done a contrast enhanced DE-CBCT. Our estimated necessary sample size is 29 subjects, taking algorithm optimization and potential invalid data into account.

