8.6. Primary objective

8.6.1. Ischemic stroke diagnostic accuracy

Endpoint

Accuracy of DE-CBCT ASPECTS to determine the extent and localization of ischemic stroke changes in brain tissue, using neCT ASPECTS as the reference standard.

Applicable subjects

Subjects diagnosed with ischemic stroke on CT.

Data

- ASPECTS
 - Left / Right
 - 1 to 10
 - Location - L, C, IC, I, M1, M2, M3, M4, M5, M6

Analysis

Images are evaluated by radiologists using neCT as reference standard and the ASPECTS diagnostic accuracy is defined.

Hypothesis:

$$H_0: \pi_1 \leq 0.80$$

$$H_1: \pi_1 > 0.80$$

Where π_1 is the observed ASPECTS accuracy and 0.80 is the performance goal.

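### For the ASPECTS and hemorrhage endpoints, section 8.2 aims at non-inferiority to CT, but the tests show only accuracy against neCT above a fixed 0.80 goal; the implied 20-point margin is neither stated nor justified.

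*Combined protocol and SAP*

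**What the plan says.** Section 8.2 gives the purpose of the sample size: it "aims to prove diagnostic quality non-inferiority compared to CT according to performance goals below". For the primary endpoint it then states "it is estimated that a sample size of 137 is required", counted in ASPECTS regions, for a "power of 90% (target accuracy of 0.90, performance goal lower boundary of 0.80, one-sided alpha of 0.025". At ten regions per subject, "a minimum sample size of 14 subjects is required".

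Section 8.6.1 defines the primary endpoint as the accuracy of DE-CBCT ASPECTS, "using neCT ASPECTS as the reference standard". The analysis text reads "Images are evaluated by radiologists using neCT as reference standard and the ASPECTS diagnostic accuracy is defined". The hypotheses are H0: π1 ≤ 0.80 and H1: π1 > 0.80, where π1 "is the observed ASPECTS accuracy and 0.80 is the performance goal". Section 8.7.2 has the same structure for the presence of intracranial hemorrhage, with neCT as reference and the same 0.80 goal.

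Section 8.7.1 (vessel visibility) is built differently. Readers rate each arterial region inferior, equal or superior to CTA, and the test concerns the share rated equal or superior.

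Under section 8.1, DE-CBCT data are "evaluated by three independent neuroradiologists (not involved in the clinical investigation"). For the primary and hemorrhage endpoints, DE-CBCT and reference images are stripped of acquisition information and read in random order, separated in time. Section 8.3 provides for kappa on interrater and within-observer agreement where applicable.

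**The concern.** A non-inferiority claim compares two methods against something that can judge both, within a margin chosen and defended in advance. For the ASPECTS and hemorrhage endpoints the plan has neither element. neCT is the truth, so its own reading performance is never estimated, and no margin is named. The only threshold is 0.80, and the plan gives no reason for that value.

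What is at stake is the meaning of a pass. If two readers of the same neCT typically agree on 95% of regions, a DE-CBCT agreement of 0.88 is a visible loss. If they agree on 85%, the same 0.88 is as good as CT can do against itself. The planned tests give the same answer in both situations, yet section 8.2 labels that answer non-inferiority to CT.

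**Working it through.** **1. Do the stated sizes come from a comparison with CT?**

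Inputs from section 8.2 for the primary: p0 = 0.80, p1 = 0.90, one-sided alpha 0.025, power 90%.

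Normal formula for one proportion against a fixed value:

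n = [z(1−α)·√(p0(1−p0)) + z(power)·√(p1(1−p1))]² / (p1 − p0)²
= [1.960 × 0.400 + 1.282 × 0.300]² / 0.10² = 136.5, so 137.

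Exact binomial tests give:

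| Endpoint | Stated n | Pass at | Exact alpha | Exact power |
|---|---|---|---|---|
| ASPECTS accuracy | 137 regions | 119 (0.869) | 0.0245 | 0.910 |
| Vessel visibility | 126 regions | 111 (0.881) | 0.0118 | 0.809 |
| Hemorrhage accuracy | 20 subjects | 20 of 20 | 0.0115 | 0.998 |

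All three sizes reproduce as single-proportion tests against 0.80. No CT performance figure and no margin against CT enters any of them.

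**2. What does a pass establish about CT?**

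For a yes/no call, two methods can differ in overall accuracy only where their calls differ. Against any truth,

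|accuracy(CT) − accuracy(DE-CBCT)| ≤ 1 − agreement.

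With agreement above 0.80, the deficit is below 1 − 0.80 = 0.20. That is the implied margin. At an agreement of exactly 0.80, DE-CBCT accuracy could lie in these ranges, with CT's true accuracy assumed because the documents do not give it:

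| CT accuracy (assumed) | Possible DE-CBCT accuracy |
|---|---|
| 0.95 | 0.75 to 0.85 |
| 0.90 | 0.70 to 0.90 |
| 0.85 | 0.65 to 0.95 |

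**3. How much disagreement passes?**

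The 14 subjects give 14 × 10 = 140 regions. Treating regions as independent, as the plan does, the exact cut-off is 122 of 140 (alpha 0.0185). So 140 − 122 = 18 regions (12.9%) may differ from neCT and the primary still passes.

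| True agreement (assumed) | Pass probability | Gap to a repeat neCT read at 0.95 (assumed) | Gap to a repeat neCT read at 0.85 (assumed) |
|---|---|---|---|
| 0.85 | 0.28 | 10 points | 0 |
| 0.88 | 0.68 | 7 points | none (3 points better) |
| 0.90 | 0.89 | 5 points | none (5 points better) |

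The pass probability does not depend on the last two columns. The design cannot tell them apart, because neCT-versus-neCT agreement is not part of it.

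For hemorrhage, a pass at 20 subjects needs 20 of 20, so the observed disagreement is zero. The guaranteed bound is nevertheless only just above the goal: 0.0125^(1/20) = 0.803.

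**The case against.** The strongest reply is that the sentence in 8.2 limits itself to the performance goals that follow, so the plan in effect defines non-inferiority as exceeding 0.80. With CT at 1.00 by construction, H1: π > 0.80 is formally a non-inferiority test with a 0.20 margin. That stands. A reader might infer that the design has no non-inferiority property at all; the documents do not support this, because a pass does cap the overall accuracy deficit at 20 points. But calling 0.80 a performance goal does not state or justify it as a margin against CT.

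A reader might also extend the point to all three tests. It does not reach vessel visibility, where sections 5.2 and 8.7.1 define the term as equal or superior to CTA and readers see both image sets together.

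Nor do the documents show that the study will report these two endpoints as non-inferior to CT. Sections 5.1, 5.2, 8.6.1 and 8.7.2 word them as accuracy against neCT, and the study calls itself a proof of concept. The broad aim stands in one sentence of 8.2. The risk is that this sentence carries into the report.

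The 0.68 pass probability is not an error rate: at a true agreement of 0.88 the null hypothesis is false and the test works as planned. Any 7-point deficit follows from two assumed values.

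Section 8.3 does foresee kappa, along with sensitivity and specificity. These apply only where applicable and are not tied to repeated neCT reads or to the 0.80 goal, so they soften the gap without closing it.

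**Conclusion.** The point holds for the primary and hemorrhage endpoints. Section 8.2 states a stronger aim than their tests can deliver: a pass shows accuracy against neCT above 0.80, which is non-inferiority in overall accuracy only at an unstated and unjustified 20-point margin, with no benchmark from a second neCT read. Vessel visibility is unaffected.

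This is a mismatch between claim and test, not an arithmetic error: 137, 126 and 20 all reproduce, and no hypothesis or decision rule has to change. The size rests on assumptions. At 140 independent regions the pass probability is 0.28, 0.68 and 0.89 at assumed true agreements of 0.85, 0.88 and 0.90. Whether those levels are worse than CT depends on a repeat-read agreement that the documents do not give.

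**What to change.** **Wording.** In section 8.2, and in the conclusion drawn for these two endpoints, replace the non-inferiority aim with *accuracy against neCT above a 0.80 performance goal*. This matches sections 5.1, 8.6.1 and 8.7.2. Leave the vessel endpoint as it is.

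**Supportive analysis.** Section 8.1 implies, but does not spell out, that each of the three readers scores both DE-CBCT and masked neCT; confirm this first. If so:

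- Report neCT-versus-neCT inter-reader agreement per region beside DE-CBCT-versus-neCT agreement.
- Score each reader's DE-CBCT call and the same reader's masked neCT call against the other readers' neCT calls.
- Use all regions, not only those where the other readers agree, since dropping the difficult regions is likely to raise measured agreement.
- Give the paired difference with a 95% interval clustered by subject.
- Show criterion 3.II subjects separately if their reference neCT is the admission scan. Their DE-CBCT is done on day 2 (section 6.5), so the difference would otherwise mix stroke evolution with modality. Section 8.6.1 does not say which neCT is used.

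**Cost.** A change of wording and one analysis, with no new scans or subjects, and no new reads if the reading scheme is as implied. The claim becomes more modest, and with 14 to 20 subjects the interval will be wide.
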